30 September 2020

Effects of Multimodal Exercises Integrated With Cognitive-behavioral Therapy in Subjects With
Chronic Neck Pain: a Randomized Controlled Study With One Year Follow-up

NCT ID not yet assigned

STUDY PROTOCOL

1. Background

The etiology of neck pain is multifactorial and includes age, sex, poor postures, repeated strains (1). Studies based on the bio-psychosocial model also link chronic neck pain to psychological factors. Among these, kinesiophobia has been reported as a significant factor (2,3). It is debatable whether interventions targeting cognitive processes and pain-associated behaviors can lead to clinically significant changes in terms of disability, pain and quality of life (4). Furthermore, there is uncertainty about the effectiveness of different types of exercises that can be proposed. This makes it difficult to choose between general exercises (aimed at improving cervical muscle and joint skills) and motor-oriented (or task-oriented) exercises (aimed at cervical functional recovery in an ecological context) (5). Over time, the use of multidisciplinary interventions for chronic vertebral pain (instead of segmental treatments) has grown in order to improve disability, pain and proactive behaviors towards the presented problem (6-9).

A recent review of the literature found that the rehabilitation treatment of neck pain with a cognitive-behavioral approach induces changes (in terms of short-term pain relief) compared with no treatment; however, these effects were not clinically significant (10).

In a randomized clinical trial authors evaluated the effectiveness of a multidisciplinary intervention compared to a short intervention, with the purpose of evaluating return to work, after one year, in subjects with neck and shoulder pain/disability; however, the results did not show significant differences between the two groups (11).

In a recent review of the literature the importance of multidisciplinary interventions also emerged for people in the workplace in order to improve pain, disability, thoughts and wrong behaviors (12).

Given these premises, it appears necessary to conduct studies aimed at evaluating the effectiveness of a multidisciplinary rehabilitation program that integrates cognitive-behavioral therapy focused on kinesiophobia with specific exercises in the treatment of workers with chronic neck pain.

2. Hypothesis

The hypothesis is that a multidisciplinary rehabilitation program induces clinically significant and long-term improvements in the disability, pain and quality of life of workers with chronic neck pain and that these would be maintained in the long term.

3. Objectives of the study

Primary objective: to verify the efficacy of a multidisciplinary program in inducing clinically meaningful and long-term improvements through changes in scores in disability assessment scales (Neck Disability Index, Tampa scale of Kinesiophobia, Pain Catastrophising Scale), in pain (Numeric Rating Scale) and in the quality of life (Short Form-36 Health Survey) of workers suffering from chronic neck pain.

Secondary objective: to evaluate changes in work discomfort (Work Ability Index, Anamnestic survey of the upper limbs and spine's pathologies) linked to the condition of chronic neck pain.

4. Methods

A randomized, parallel-group superiority-controlled trial will be conducted in a secondary care rehabilitation hospital and approved by the hospital's Institutional Review Board (ID: PG/2020/16818; date of approval: 30 september 2020).

a) Participants

The inclusion criteria will be a diagnosis of non-specific chronic neck pain (i.e. a documented history of pain lasting >3months), a good understanding of Italian and an age of >18years.

The exclusion criteria will be acute and subacute neck pain, cognitive impairment and all causes of specific neck pain (i.e. previous spinal surgery, deformity, disc herniation, infection, fracture, myelopathy or malignancy, whiplash injuries, and systemic or neuromuscular diseases) ruled out by means of case histories and imaging. Any subjects who had previously received cognitive-behavioural therapy will be also excluded.

Outpatients visiting the hospital between September 2020 and December 2021 will be evaluated by two physiatrists coordinated by the principal investigator. Those who meet the inclusion criteria will be asked to declare their willingness to comply with any treatment option, to which they will be randomly assigned. Once the patient gave their consent, the biostatistician will randomize the subject to one of the two treatment programmes using a permuted-block randomization procedure. The list of treatment codes will be previously generated and stored in Matlab and an automatic assignment system, also developed in Matlab, will be used to conceal the allocation. The principal investigator obtaining and assessing the data and the biostatistician making the analyses will be blinded to treatment allocation. The physiotherapists, the psychologist and the patients will not be blinded.

b) Interventional programmes

Interventions will be delivered by a psychologist and two equally experienced physiotherapists, separately responsible for the multidisciplinary and the general exercise group. Each participant will be evaluated individually by means of postural observation, cervical range of motion examination, manual muscle testing. Based on this evaluation, the exercises will be planned and carried out for each patient. Given that the Italian National System allows for 10 rehabilitative sessions for outpatients and owing to the complex nature of chronic complaints, the physiotherapists will arrange one 60-minute session of physical training per week for ten weeks and will ask the patients to repeat the exercises at home. The multidisciplinary group will meet with the psychologist once a week for a 60-minute session as described below. Thus, the multidisciplinary programme will last for a total of 20 hours, while the general exercise programme will last for 10 hours.

c) Multidisciplinary group

Multimodal exercises will be first introduced to improve, by means of graded exposure, cervical mobility, postural control, strengthening muscles and stretching the neck. Patients will learn stabilizing techniques for neck deep muscles, progressively increasing the speed and complexity of the movements. Subsequently, task-oriented exercises while maintaining spinal deep muscle activation will be introduced. Under the supervision of the psychologist, subjects will also be involved in group-based cognitive-behavioural therapy aimed at

modifying fear of movement and maladaptive illness behaviour. The situations to handle will be identified on the basis of the fear-avoidance beliefs emerging from the group discussion of the activities more frequently reported, the administered questionnaires and the presentation of images showing neckstressing activities.

d) General exercise group

General physiotherapy will include exercises for muscle strengthening, regional stretching and spinal mobilization.

e) Both groups

Ergonomic advice was provided by means of a booklet given to the participants during the first session in order to facilitate the modification of daily living activities. At the end of treatment, patients were asked to continue with the exercises at home. A fidelity check, based on a manual including the complete list of exercises to be delivered, will be conducted at the end of each session to verify that all of the planned exercises will be actually performed.

No other treatments (e.g. physical modalities, nerve blocks, pharmacological agents) will be offered. Family doctors will be asked to avoid referrals for other treatments while the participants will be undergoing the programmes.

f) Type of data collected

- Demographic, anthropometric and clinical characteristics of the participants
- Disability (primary outcome): assessed using the validated Italian version of the self-reported 10-item Neck Disability Index (13).
- Kinesiophobia: assessed using the validated Italian 13-item version of the self-report Tampa Scale for Kinesiophobia (14).
- Catastrophizing: evaluated by means of the 13-item validated Italian version of the self-reported Pain Catastrophizing Scale (15).
- Pain intensity: assessed using an 11-point numerical rating scale (16).
- Quality of life was assessed using the Italian version of the self-report Short-Form Health Survey (17,18).
- Work ability: assessed using Work Ability Index (19).

- Anamnestic and clinical evaluation of the pathologies affecting the upper limbs and spine (20).

The questionnaires will be completed before treatment, ten weeks later (posttraining), and 12 months after the end of treatment (follow-up). At the end of treatment, the subjects will be also asked to rate the effectiveness of the treatment using the 5-point Likert Global Perceived Effect scale (21). Using a specific form, patients were asked to report any symptoms they experienced during the study that required further treatment.

5. Sample size and statistical analysis

The sample size will be computed using the Italian Neck Disability Index, for which it will be estimated that a between-group difference of 7 points should be considered as clinically important (22). In order to assure 80% statistical power and 5% type I error, and considering a standard deviation of 15.4 points, 154 patients will be required, but 170 will be recruited to allow for a drop-out rate of 10%. The differences between the two groups relating to measures with non-normal distribution will be analyzed by Mann-Whitney U test. The null hypothesis will be rejected for p values > 0.05 (two-tailed test).

References

- 2) Hudes K. The Tampa Scale of Kinesiophobia and neck pain, disability and range of motion: A narrative review of the literature. *J Can Chiropr Assoc* 2011; 55(3): 222–232.

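### The hypothesis is about clinically significant improvement, but the planned analysis yields only a p value and no NDI difference with a confidence interval to set against the plan's own 7 points

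*Combined protocol and SAP*

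**What the plan says.** Section 2 (Hypothesis) states that the programme "induces clinically significant and long-term improvements in the disability, pain and quality of life of workers with chronic neck pain". Section 3 sets the primary objective in the same terms: "to verify the efficacy of a multidisciplinary program in inducing clinically meaningful and long-term improvements through changes in scores in disability assessment scales". The design in section 4 is plain superiority, with no margin: "A randomized, parallel-group superiority-controlled trial will be conducted in a secondary care rehabilitation hospital". Section 4(f) names the primary outcome: "Disability (primary outcome): assessed using the validated Italian version of the self-reported 10-item Neck Disability Index".

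Section 5 gives the only numerical meaning of clinical importance, that "a between-group difference of 7 points should be considered as clinically important". It uses this value to size the trial for "80% statistical power and 5% type I error". The analysis text that follows has two elements. One is a test: "The differences between the two groups relating to measures with non-normal distribution will be analyzed by Mann-Whitney U test". The other is a two-tailed rejection rule at 0.05. No test is named for normally distributed measures. No effect estimate, confidence interval or primary time point is given.

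**The concern.** The question is framed clinically, and the plan supplies a clinical yardstick for its primary outcome. Yet nothing in the stated analysis produces a quantity that can be held against it. A p value says whether the data are compatible with no difference; it does not say how large the difference is. The Mann-Whitney test compares ranks. A shift estimate could be attached to it, but none is planned.

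At stake is what the trial can say at the end. If the result is significant but modest, the plan does not say how it will be read against 7 points, so that reading would be chosen after the data are known. The same applies to a non-significant result whose interval still includes 7. The Global Perceived Effect scale is collected at the end of treatment, but no interpretation rule is attached to it, so it does not fill the gap.

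**Working it through.** **Inputs from section 5:** planning difference 7 points; SD 15.4; power 80%; type I error 5%, two-tailed; 154 evaluable, 170 recruited.

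**Assumptions:** 1:1 allocation (the ratio is not stated); p < 0.05 is the intended rule; NDI means are compared (the plan does not say so).

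**1. The plan's sample size.** By the normal approximation, n per arm = 2 × (1.960 + 0.842)² × 15.4² / 7² ≈ 2 × 7.85 × 4.84 ≈ 76, or 152 in total. The two-sample t-test gives 77 per arm, 154 in total, with power 80.03%. The stated 154 is reproduced. For drop-out, 154 × 1.10 = 169.4, rounded up to 170.

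**2. Smallest significant observed difference, 77 per arm.**
- Standard error = 15.4 × √(2/77) = 2.48 points.
- Critical value t(0.975, 152 df) = 1.976.
- Smallest significant difference = 1.976 × 2.482 = 4.90 points, and 4.90 / 7 = 0.70.
- 95% confidence interval at that result: 4.90 ± 4.90, about 0 to 9.8.
- For comparison, an observed difference of exactly 7 has an interval of 7 ± 4.90, about 2.1 to 11.9.

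A result at the edge of significance is therefore compatible with almost no effect and with an effect well above 7. Only the interval shows this.

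**3. How often a significant result would fall below 7** (normal approximation, SE 2.48).
- True difference 5: P(significant for the programme) = 1 − Φ(1.96 − 5/2.48) ≈ 52%. P(significant and estimate below 7) = Φ((7 − 5)/2.48) − Φ((4.86 − 5)/2.48) ≈ 31%.
- True difference 7: P(significant) ≈ 80.5%. P(significant and estimate below 7) ≈ 30.5%.

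**4. Sensitivity of the smallest significant difference.**

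| SD | Per arm | Points |
|---|---|---|
| 10 | 77 | 3.2 |
| 12 | 77 | 3.8 |
| 15.4 | 77 | 4.9 |
| 15.4 | 85 (no drop-out) | 4.7 |
| 18 | 77 | 5.7 |

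It is below 7 throughout. Baseline adjustment would lower it further to the extent that baseline and follow-up NDI are correlated; the documents give no correlation, so this is not sized.

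**The case against.** The strongest reply is that this is ordinary superiority design: size the trial on the important difference and test against zero. At 80% power and two-sided 5%, the smallest significant difference is always about 1.96 / 2.80 = 70% of the planning difference. The 4.9 against 7 is thus a property of every trial planned this way. That stands in full, and a reader who infers from it that the sample size is wrong or too small would be mistaken.

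A reader might also infer that the plan treats p < 0.05 as proof of clinical significance and would declare its hypothesis confirmed at 4.9 points. The documents do not say this. Section 5 says when the null hypothesis is rejected and is silent on how the result is then interpreted. Silence is the defect, and it is a weaker one.

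Three narrower points also stand. The Mann-Whitney test is reserved for non-normal measures, and whether NDI is one of them is unknown. The 4.9 comes from a comparison of means that the plan does not name. The hypothesis names no comparator, so taking the between-group 7 points as its yardstick is an interpretation; the superiority design and section 5 make it the natural one.

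What survives is that a trial posing a clinical question, with a stated clinical value, plans no output that can be compared with that value.

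**Conclusion.** The point holds as a gap in estimation and interpretation. It affects what may be claimed and leaves the validity of the comparison and the sample size untouched. Its size: under a comparison of means with SD 15.4, 77 per arm, 1:1 allocation and p < 0.05, significance begins at about 4.9 NDI points, with an interval of about 0 to 9.8. At a true difference of 5, roughly three trials in ten would be significant with an estimate below 7.

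Two further inferences are not supported. One is that the trial could repeat the earlier cognitive-behavioural finding described in section 1. That finding concerned short-term pain relief against no treatment; here the primary outcome is disability and the comparator is general exercise. The other is that a hard threshold is needed:
- Requiring an estimate of at least 7 would be met only 50% of the time at a true difference of 7.
- Requiring the lower limit to exceed 7 would need an observed difference of about 11.9 (7 + 4.9), with about a 2.5% chance at a true difference of 7.
- Counting individuals who improve by 7 points would give the value a meaning that section 5 does not; it defines 7 only as a between-group difference.

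**What to change.** In section 5, state that:

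- the primary result is the between-group mean difference in NDI, adjusted for baseline NDI, with its 95% confidence interval;
- it is taken at one named time point, which should be the 12-month follow-up if the long-term hypothesis is primary;
- it is reported beside the 7-point value;
- p < 0.05 supports a statement of superiority only;
- any statement about clinical significance is based on where the estimate and interval lie relative to 7, and not on the p value.

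The Mann-Whitney test can remain as a supporting analysis if NDI is markedly non-normal. The direction of the printed p-value rule needs correcting separately.

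The cost is a few lines of analysis text. Baseline and follow-up NDI are already collected, and the sample size does not change. The downside is that some significant results could be called superior without being called clinically significant.

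### The only harm record admits a symptom only if it needed further treatment, so transient or untreated symptoms need not be counted in either arm

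*Combined protocol and SAP*

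**What the plan says.** Section 4 f) (Type of data collected) ends with the only item that works as a harm record. Using a dedicated form, "patients were asked to report any symptoms they experienced during the study that required further treatment". No collection times are given for this form.

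Other provisions bear on the point:

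- **Section 4 e) (Both groups), co-treatment.** Within the trial, nothing beyond the two programmes is provided, with physical modalities, nerve blocks and drugs given as examples. For care outside the trial, the plan adds a request: "Family doctors will be asked to avoid referrals for other treatments while the participants will be undergoing the programmes".
- **Section 4 e), session check.** A fidelity check at the end of each session verifies that the planned exercises were done. It is not described as asking about symptoms.
- **Section 4 f), other measures.** These include the Neck Disability Index, an 11-point pain scale and an evaluation of upper-limb and spine disorders. Questionnaires are completed at baseline, at ten weeks and 12 months after treatment ends.
- **Section 4 b) (Interventional programmes), exposure.** Patients have "one 60-minute session of physical training per week for ten weeks". In total, "the multidisciplinary programme will last for a total of 20 hours, while the general exercise programme will last for 10 hours".
- **Section 4 c) (Multidisciplinary group), progression.** Patients learn stabilising techniques for the deep neck muscles, "progressively increasing the speed and complexity of the movements".
- **Section 4 a) (Participants), blinding.** "The physiotherapists, the psychologist and the patients will not be blinded".

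The documents contain no adverse-event definition, no severity or causality grading, and no harms analysis by arm.

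**The concern.** An entry condition decides what can ever be counted. Here a symptom qualifies by its consequence (it needed treatment), not by having occurred. With an exercise programme that is progressed over ten weeks, plausible unwanted effects include a flare of neck pain, arm symptoms or dizziness. Some of these would settle, some would be put up with, and some might lead a patient to skip sessions or stop. None of these outcomes is in itself a need for further treatment.

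What is at stake is the harm side of the comparison. The primary efficacy analysis is not affected. A short or empty list of symptoms could reflect the threshold as much as the programmes, and a transient symptom that was never recorded cannot be recovered at analysis.

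**Working it through.** The plan gives no harm rate or harm count to reproduce, so the check is mainly a reading of the text, followed by an illustration on assumed figures.

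**Step 1. What the form admits.** Apply the entry condition in section 4 f) to four cases:

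| Symptom during the programmes | Falls within the form's wording? |
|---|---|
| Needed treatment and was treated | Yes |
| Judged by the patient to need treatment, but not treated | Yes, because the wording concerns need, not receipt |
| Endured or settled, not judged to need treatment | No |
| Led to missed or stopped sessions, not judged to need treatment | No |

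The last two rows are lost through the threshold alone, in both arms.

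**Step 2. Whether another item fills the gap.** The disability index, the pain scale and the upper-limb and spine evaluation can show a worse state at ten weeks or at 12 months after treatment. They cannot show an episode that began and ended between assessments, when it happened, or whether a session brought it on. The session check could show that an exercise was left out, but not that a symptom was the reason. The global rating at the end of treatment asks about effectiveness.

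**Step 3. How section 4 e) interacts.** The trial offers no other treatment, and family doctors are asked not to refer during the programmes. This may make a patient less likely to seek care, or to regard a symptom as needing it. It is a request, and it leaves the form open to anyone who judges that treatment was needed.

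**Step 4. Illustration (assumed rates).** The only input from the plan is the recruitment target of 170 (section 5). The allocation ratio is not stated; assuming 1:1 gives 170 / 2 = 85 per arm. Let p be the true proportion of patients with a symptom and c the share of them whom the form records. Both are assumptions.

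- Expected number recorded in one arm = 85 × p × c
- Probability that the arm records none = (1 − p × c)^85

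| p | c = 100% | c = 50% | c = 25% | c = 10% |
|---|---|---|---|---|
| 5% | 4.25; 1.3% | 2.1; 11.6% | 1.1; 34.3% | 0.43; 65.3% |
| 10% | 8.5; 0.013% | 4.25; 1.3% | 2.1; 11.6% | 0.85; 42.6% |
| 20% | 17; below 0.001% | 8.5; 0.013% | 4.25; 1.3% | 1.7; 18.0% |

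Each cell gives the expected count, then the chance of a zero count. For example, with p = 10% and c = 10%: 85 × 0.10 × 0.10 = 0.85, and 0.99^85 = 0.426.

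The recorded proportion is p × c, so it understates p by the factor c. That restates the assumption and does not estimate c. An empty arm becomes likely only when symptoms are uncommon or capture is low; at p = 10% with half captured, the form would still be expected to record about four patients.

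**The case against.** The strongest reply is that the form is compatible with the rest of the plan and that the plan is not blind to deterioration. Four parts of it deserve an answer.

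1. **Sections 4 e) and 4 f) do not conflict.** A reader might infer that the plan suppresses its own reporting trigger, because it offers no treatment and discourages referral while counting only symptoms that needed treatment. The documents do not support this. Needing treatment is not the same as receiving it, nothing stops a patient from seeking care, and the request to family doctors covers only the programme period. The form can even show where outside treatment was needed despite the request. This part stands: section 4 e) may lower recording, but it does not prevent it.

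2. **Lasting worsening is measured.** True, and arm symptoms fall within the subject of the upper-limb and spine evaluation. Transient events, their timing and their cause remain uncaptured.

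3. **No harms comparison and no tolerability claim are planned.** Also true: the objectives in section 3 concern efficacy and work discomfort. Power to compare symptom rates is therefore not a property of this plan, and none is claimed here. The plan nevertheless collects harm information in a form that will be hard to interpret if it is reported.

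4. **The form itself is not in the documents.** Its actual layout could be broader than the one-sentence description. If so, the description should be brought into line with it.

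**Conclusion.** The point holds as a limitation of the reporting threshold. The only harm-related record excludes symptoms not judged to need further treatment, and no other item in the plan records transient symptoms. This follows from the wording alone and needs no assumed rate.

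The size is unknown. The illustration rests on assumed symptom rates, assumed capture shares, 1:1 allocation and all 170 recruited patients contributing. With 154 / 2 = 77 per arm the counts fall in proportion: at p = 10% with full capture, 7.7 instead of 8.5. It shows only that a sparse symptom table could arise from the definition.

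A reader might also infer that the threshold biases the comparison between arms, since patients are unblinded and contact time is 20 hours against 10. That is possible, but the documents give nothing from which to establish its presence or direction. Any statement that the programmes were well tolerated would need to acknowledge the threshold. The change is a cheap improvement.

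**What to change.** In section 4 f), and on the form:

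- Record any new or worsened symptom, whether or not it was treated, with its date, its severity, and whether sessions were missed or stopped because of it.
- Keep the need for further treatment as a severity flag instead of the entry condition.
- State when the form is given: at least at the existing ten-week and 12-month assessments, in both arms, and if feasible alongside the existing end-of-session check. The last of these would serve transient symptoms best.

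In section 5, add a descriptive table of the number of patients with at least one symptom, and with at least one that needed treatment, by arm and by period (programme, follow-up).

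The cost is a reworded form, a stated schedule where none exists now, slightly more form-filling and one table. More minor soreness will be recorded, so the symptom rate will look less favourable. Neither the treatments nor the request to family doctors changes.

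### The plan allows for drop-out only by recruiting more patients: it does not say that those who stop will be followed or analysed, and the 12-month visit has no clear date for them

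*Combined protocol and SAP*

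**What the plan says.** Section 5 sizes the trial on the patients who remain: "154 patients will be required, but 170 will be recruited to allow for a drop-out rate of 10" per cent. It does not say whether a drop-out has left the sessions or left the study. It names one test, Mann-Whitney, for measures that are not normally distributed. It does not name an analysis population or a way of handling missing scores.

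Section 4 f sets the assessments: "The questionnaires will be completed before treatment, ten weeks later (posttraining), and 12 months after the end of treatment (follow-up"). The Global Perceived Effect rating is also taken when treatment ends. The primary outcome, the NDI, is completed by the patient.

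Section 4 b gives the contact time: "Thus, the multidisciplinary programme will last for a total of 20 hours, while the general exercise programme will last for 10 hours". Section 4 a states that patients, physiotherapists and the psychologist are not blinded. The investigator who obtains and assesses the data and the analysing biostatistician are stated to be blinded.

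**The concern.** Recruiting extra patients restores precision. It does not restore the comparability that randomisation gave, if those who leave differ from those who stay and the loss is uneven between arms. Uneven loss is plausible here, because one programme asks for twice the contact time of the other and patients know which one they have.

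The schedule adds to the problem. A patient who stops in week 3, or never attends, has no obvious end of treatment from which to count 12 months. Local staff could reasonably conclude that no follow-up form is due. The hypothesis in section 2 concerns improvement that lasts, so this is the visit that carries the long-term claim. An analysis population can be written late, but a score that was never requested cannot be recovered.

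**Working it through.** **Inputs.** From section 5: "a between-group difference of 7 points should be considered as clinically important"; "In order to assure 80% statistical power and 5% type I error, and considering a standard deviation of 15.4 points"; "two-tailed test"; 154 required, 170 recruited, 10% drop-out. From section 4 a: "one of the two treatment programmes using a permuted-block randomization procedure". The allocation ratio is not stated, so 1:1 is assumed, giving 85 per arm.

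**The plan's own figure.** n per arm = 2 × (1.96 + 0.842)² × (15.4 / 7)² = 75.98, so 76 per arm and 152 in total. The t-test version gives 76.95, so 77 per arm and 154 in total, as stated. Then 154 × 1.10 = 169.4, rounded up to 170. The sample-size calculation is not at fault. It does confirm that power was set on the patients left after drop-out.

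**Which assessments can be dated for a patient who stops early.**
- Baseline: yes, it precedes treatment.
- Ten weeks: yes, it is an interval, and the post-training tag is only a label.
- 12-month follow-up: unclear, because it is counted from the end of treatment.
- Global Perceived Effect: unclear, for the same reason.

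**Bias if only observed scores are compared.** Let p1 and p0 be the drop-out proportions in the multidisciplinary and general exercise arms. Let patients who stop score D points worse than completers in the same arm. If completers average C, the whole arm averages C + pD, so using completers alone flatters that arm by pD. The bias in favour of the multidisciplinary arm is therefore (p1 − p0) × D.

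The documents give neither drop-out by arm nor D, so both are assumptions. The splits below average the planned 10%, and D is 10 or 15.4 points (one SD). The standard error is 15.4 × √(1/n1 + 1/n0), with n1 = 85(1 − p1) and n0 = 85(1 − p0). The type I error is Φ(−1.96 + |bias|/SE) + Φ(−1.96 − |bias|/SE).

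| Drop-out, multidisciplinary vs general | SE | D | Bias (points) | Share of 7 points | Two-sided type I error |
|---|---|---|---|---|---|
| 10% vs 10% | – | 10 or 15.4 | 0 | 0 | 5% |
| 15% vs 5% | 2.49 | 10 | +1.0 | 14% | 6.9% |
| 15% vs 5% | 2.49 | 15.4 | +1.5 | 22% | 9.5% |
| 5% vs 15% | 2.49 | 10 | −1.0 | 14% | 6.9% |
| 5% vs 15% | 2.49 | 15.4 | −1.5 | 22% | 9.5% |
| 20% vs 0% (extreme) | 2.51 | 10 | +2.0 | 29% | 12.6% |
| 20% vs 0% (extreme) | 2.51 | 15.4 | +3.1 | 44% | 23.3% |

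The two reversed rows have the same size and the opposite sign: they count against the multidisciplinary arm.

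**Power if everyone is analysed.** With 85 per arm, power = Φ(Δ / (15.4 × √(2/85)) − 1.96), where 15.4 × √(2/85) = 2.362. For Δ = 7 this is 84.2%. If counting patients who stopped reduced the difference by 5% (6.65 points) it is 80.4%, and by 10% (6.3 points) 76.0%. The dilution is an assumption, and the SD is held at 15.4.

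**The case against.** The strongest reply is that the plan is silent rather than wrong. Raising recruitment for expected drop-out is routine, including in trials analysed by intention to treat, and it excludes nobody. Four stronger readings are tempting, and the documents do not support them.

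- A reader might infer that the plan gives up on drop-outs and will produce a completers analysis. No section says so. The silence permits such an analysis but does not prescribe it.
- A reader might infer that the whole assessment schedule hangs on the treatment course. It does not: the baseline and ten-week questionnaires can be dated for anyone.
- A reader might infer that the comparison as a whole is unblinded. Patients and therapists are, which matters for a self-reported score, but the data assessor and the analysing biostatistician are stated to be blinded.
- A reader might infer that the bias favours the multidisciplinary programme. That needs more drop-out in that arm and worse scores among those who leave. Patients given the shorter programme might leave more often, and some patients may stop because they feel better.

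Two further points have some force. Entrants must say that they will accept either programme, which gives some protection against leaving because of allocation, although the plan still expects 10% to drop out. And a rank test does not in itself fix the analysis population: it can be given imputed scores or changes from baseline, and the plan does not say that the NDI will be treated as non-normal. But it provides for neither imputation nor baseline, and it names no other test.

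What stands is the omission: no analysis population, no missing-data rule, no undertaking to follow patients who stop, and an unclear anchor for the 12-month visit.

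**Conclusion.** The concern holds as an omission that should be corrected while scores can still be collected. A moderately uneven loss of 15% against 5% would move the NDI difference by 1.0 to 1.5 points, or 14% to 22% of the target, and raise a nominal 5% error rate to about 7% to 9.5%. The larger figures in the table need an extreme split and mark an outer bound. All of these rest on assumed drop-out by arm, an assumed 10 to 15.4 point deficit in those who stop, 1:1 allocation and the plan's SD. The direction of any bias is unknown, and with equal drop-out and equal outcomes there is none. The case for change does not depend on the direction: following everyone and using all three NDI scores improves on the stated method either way.

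**What to change.** 1. In section 4 f, state that the questionnaires are sought from every randomised patient at ten weeks and at a 12-month visit, whether or not they attend sessions. Date the 12-month visit from randomisation or from the scheduled end of the ten-week course. Data collection ends only if the patient withdraws consent to it. Define drop-out accordingly, separating leaving the programme from leaving the study.
2. In section 5, compare NDI for all randomised patients in their assigned arm, using a mixed model on the baseline, ten-week and 12-month scores. A patient with one missing visit then still contributes, and baseline is used. Other valid methods exist. This one needs no data beyond what is already planned.
3. Report drop-out by arm with reasons. A mixed model adds little for a patient with no post-baseline score, and it does not by itself deal with loss that depends on the unseen outcome. So add a sensitivity analysis that shifts missing scores by 5, 10 and 15 NDI points in each arm in turn and in both.

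The cost is protocol and SAP wording and some extra contact effort. The estimated difference may be slightly smaller because patients who stopped now count. The recruitment target need not change for this wording alone, but the power figures above show that dilution much beyond 5% would take power below 80%.
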